1.1. Background/Rationale

Study R10933-10987-COV-2176 was terminated early by the Sponsor due to the high frequency of the Omicron variant and reduced neutralization potency of casirivimab+imdevimab against the Omicron variant. The study is not being terminated due to any safety concerns, nor from any data obtained in this study. The protocol amendment 2 followed the sponsor's decision to close enrollment early and the study was revised to allow one optional dose and obtain final safety assessments.

Optional Dose

Casirivimab+imdevimab may continue to serve as an important pre-exposure prophylaxis therapeutic among immunocompromised individuals in regions where Omicron is not the dominant variant or in regions where Omicron prevalence subsides. For this reason, participants will have the option to receive a 1200 mg SC dose of casirivimab+imdevimab as a final study dose. This optional dose may be administered to all participants regardless of treatment assignment at randomization. However, participants will not be eligible to receive this dose if they have already received casirivimab+imdevimab as post-infection treatment.

Participants will be asked to return to the site for an unscheduled visit, during which they will be asked to consent to protocol amendment 2 and receive the final optional dose, if desired. This visit to receive the final optional dose should occur approximately 4 weeks after the most recent dose. Note that consent may be obtained remotely prior to this visit, if available and allowable by the study site.

Procedures in the Event of Suspected COVID-19

Participants with suspected COVID-19 may undergo an optional visit to evaluate symptoms by a study clinician (investigator or designee) and to undergo laboratory testing of SARS-CoV-2, as detailed in the new schedule of events (protocol amendment 2 Table 2). This optional visit

should occur as soon as possible (within 48 hours of symptom onset, if feasible). Note that clinician assessment of sign or symptoms may occur remotely. If remote assessment is performed, a confirmatory site visit for laboratory testing of SARS-CoV-2 can optionally occur after a clinician deems that the signs or symptoms are related to COVID-19.

Clinical Evaluation:

Signs and symptoms will be evaluated by a clinician (investigator or designee, evaluation may occur remotely) as described below (in the Documentation of Clinical Evaluation section). If the clinician confirms that at least one sign or symptom is potentially related to COVID-19, samples may be collected to perform both local and central testing for SARS-CoV-2 infection.

Laboratory Testing of SARS-CoV-2:

Local testing must be performed by RT-PCR using local sample collection and assay standards. A nasopharyngeal (NP) swab sample is the preferred sample type, but other samples (eg, nasal, oropharyngeal, saliva) adhering to local standards are acceptable. An additional NP swab sample will be collected for the purposes of central RT-qPCR testing. The samples will be collected prior to any administration of post-infection treatment (described below). The qualitative result of the central RT-qPCR will be reported back to the corresponding study site. SARS-CoV-2 viral genome sequencing will be performed using NP swab samples collected during the study that have been confirmed positive by RT-qPCR at the central laboratory.

Documentation of Clinical Evaluation. For each symptom, the start (onset) date, end date, and severity will be recorded (mild, moderate, severe) in the participant's medical record (source document). It is important to record this information in the source document, to ensure that the temporal dimensions of each sign or symptom are captured.

The following information may subsequently be recorded in EDC as applicable:

- The sign or symptom, with start (onset) calendar date, end calendar date, and severity (mild, moderate, severe)
- Confirmatory local RT-PCR test result and date of sample collection
- Confirmatory central RT-qPCR test result and date of sample collection
- Weekly central RT-qPCR test results and dates of sample collection
- Record of any post-infection treatment with casirivimab+imdevimab administered

Note that any sign or symptom considered by the investigator to be unrelated to baseline conditions and unrelated to treatments for baseline conditions will also be recorded and used for safety evaluation.

Post-Infection Treatment. Participants with confirmed positive SARS-CoV-2 RT-PCR will be eligible for post-infection treatment (as described in protocol Section 6.4.4) at any time prior to receipt of the optional 1200mg SC dose (eg, during the 4 weeks between receipt of the last protocol-defined dose and optional 1200 mg SC dose). Once this optional dose has been

administered, post-infection treatment will no longer be offered. Likewise, any participant who receives post-infection treatment will not be eligible to receive the optional 1200 mg SC dose.

Participants with Positive SARS-COV-2 RT-PCR. Participants with a positive SARS-CoV-2 RT-PCR may have additional assessments and sample collections, including unscheduled visits every 7

days (± 1 day) for central laboratory RT-qPCR analysis until 2 consecutive negative test results are obtained:

- NP swab samples for RT-qPCR
- COVID-19 signs and symptoms evaluated by the investigator or designee
- Information regarding COVID-19-related medically-attended visits (MAVs; defined in protocol Section 9.2.4.3)

End-of-Study Visit

All participants, including those who do not consent to receive the optional final dose, will have a follow-up (end-of-study) telephone visit approximately 85 days (3 months) from their last dose of investigational drug (casirivimab+imdevimab or placebo) to monitor safety. Study assessments for the 3-month follow-up visit will be limited to the collection of targeted adverse events, as detailed in the new schedule of events (protocol amendment 2 Table 2).

Sites will ensure that an additional discussion about the potential risks and benefits to the participant and fetus is discussed as part of re-consent for participants who become pregnant during the study.

Analysis Plan

At the time that enrollment was closed, 66 participants had been enrolled in the study. Due to the early study closure and the resulting small sample size of enrolled participants, all analyses will be performed descriptively and only numeric comparisons will be performed. All safety endpoints (including AEs, TEAEs, AESIs, SAEs, and safety laboratory values) will be summarized. Selected efficacy, virology, PK, and/or immunogenicity data may also be analyzed descriptively. No interim analysis will be performed for this study, and no IDMC review meetings will occur.

The study consists of three periods: a screening period of up to 14 days, an efficacy assessment period (EAP) of approximately 6 months (precise definition below), and a 3-month follow-up period.

The primary endpoint of the study will evaluate symptomatic SARS-CoV-2 infection cases. The conditions for symptomatic SARS-CoV-2 infection are as follows:

- At least 1 sign or symptom (broad term definition) confirmed by a study clinician (investigator or designee) to be related to COVID-19, and
- A positive SARS-CoV-2 RT-PCR result (local or central analysis), with

- The sign/symptom onset date and the date of collection for the positive sample occurring within ± 7 days of one another

The primary endpoint will analyze symptomatic SARS-CoV-2 infection during the efficacy assessment period (EAP).

Broad Term COVID-19 signs and symptoms include fever $\geq 38.0^{\circ}\text{C}$ as well as 23 symptoms designed to be consistent with the Symptom Evolution of COVID-19 (SE-C19) instrument developed by the Sponsor.

Participants will be monitored for suspected COVID-19 symptoms throughout the study. Those with suspected COVID-19 will be evaluated by a study clinician for signs and symptoms of COVID-19 and will have RT-PCR testing to confirm SARS-CoV-2 infection.

The double-blind design serves to reduce potential bias introduced by knowing the study drug assignment. The comparator arm in this study will be placebo, as no approved or authorized pre-exposure preventative treatments were available at time of study initiation in the regions where the study is being conducted.

Study Population

In the absence of a universal clinical definition, this study will define an immunocompromised state according to a discrete set of primary and secondary immunodeficiencies used as eligibility criteria.

Double Blind Design

The double-blind design serves to reduce potential bias introduced by knowing the study drug assignment. The comparator arm in this study will be placebo, as no approved or authorized pre-exposure preventative treatments are currently available at time of study initiation in the regions where the study is being conducted.

Efficacy Analysis Sets

The intent-to-treat (ITT) population is defined as all randomized participants.

The primary analysis population for efficacy will be the modified intent-to-treat (mITT) population, defined as all randomized participants who received at least one dose of the study drug and at baseline (day 1):

1. Have tested negative by RT-qPCR (central lab results), and
2. Have central serology test result (ElecSys® anti-S RBD total Ig) ≤ 50 U/mL

Participants who are deemed medically ineligible or contraindicated to receiving a full course of standard-of-care COVID-19 vaccine will also be included in the mITT.

Primary Efficacy Analysis

The EAP is defined as the day 2 to day 169 visit. The cumulative incidence of cases through the EAP will be estimated using the Kaplan-Meier method, and the antibody efficacy (AbE) will be estimated as the percent risk reduction (ie, $100 \times [1-\text{HR}]$, where HR is the hazard ratio for comparison of the incidence of cases in the antibody arm versus placebo). A unstratified Cox

proportional hazard regression model with treatment group as a fixed effect will be used to estimate the hazard ratio and 95% CI (2-sided).

For the primary analysis, cases will be counted from day 2 through day 176 (ie, day 169 + 7 days), to allow for cases to accrue until the end of the EAP visit window per the Schedule of Events. Time of symptomatic SARS-CoV-2 infection will be the earlier of the sign/symptom onset date or the sample collection date for which RT-PCR result (local or central) was positive.

Safety Analyses

For safety variables, the following observation periods are defined:

The pretreatment period is defined as the time from the signing of the ICF to before study drug administration.

The EAP is defined as the day from first dose of study drug to day 169 ± 7 days

The Follow-up period is defined as the end of the EAP to the end of the Follow-up Period (ie, the last study visit).

Treatment-emergent adverse events (TEAEs) are defined as those that are not present at baseline or represent the exacerbation of a pre-existing condition.

Per protocol amendment 2, this study will collect all clinical and laboratory TEAEs that are not related to the patient's underlying (non-COVID) disease and/or not related to treatments for the underlying conditions.

Other Safety Analyses

Vital Signs, Laboratory Tests, treatment exposure, and treatment compliance analyses will be performed.

1.2. Study Objectives

1.2.1. Primary Objectives

The primary objective of the study is to evaluate the effect of casirivimab+imdevimab, compared with placebo, in preventing symptomatic SARS-CoV-2 infection in immunocompromised participants.

1.2.2. Secondary Objectives

The secondary objectives of the study are:

- To evaluate the safety and tolerability of repeated SC injections of casirivimab+imdevimab in the study population
- To characterize concentrations of casirivimab and imdevimab in serum over time
- To assess the immunogenicity of casirivimab and imdevimab

1.2.3. Exploratory Objectives

The exploratory objectives of the study are:

- To evaluate additional indicators of casirivimab+imdevimab clinical efficacy and disease prevention compared to placebo
- To evaluate the effect of casirivimab+imdevimab, compared to placebo, in preventing SARS-CoV-2 infection with elevated viral load
- To explore biomarkers predictive and/or indicative of safety and/or efficacy of casirivimab+imdevimab, COVID-19 vaccine response, SARS-CoV-2 infection and immune response, COVID-19 disease progression and clinical outcomes of casirivimab+imdevimab
- To explore the effect of baseline immune response to COVID-19 vaccination on response to casirivimab+imdevimab and clinical outcomes

1.2.4. Modifications from the Statistical Section in the Final Protocol

Some exploratory efficacy endpoints listed in protocol amendment 2 will not be reported.

1.2.5. Revision History for SAP Amendments

NA

2. INVESTIGATION PLAN

2.1. Study Design and Randomization

This is a randomized, double-blind, placebo-controlled, phase 3 study to assess the safety and efficacy of anti-SARS-CoV-2 mAb therapy, casirivimab+imdevimab as pre-exposure prophylaxis against symptomatic COVID-19 in immunocompromised individuals, defined according to the primary and secondary immunodeficiencies outlined in the study eligibility criteria. The study consists of three periods: a screening period of up to 14 days, an efficacy assessment period (EAP) of approximately 6 months and a 3-month follow-up period. A diagram depicting the study design is provided in the protocol. In addition to the main study, an optional immunology sub-study will be conducted outside of the protocol.

Participants were randomized according to a central randomization scheme using an interactive web response system (IWRS).

Randomization were stratified according to age categories (<18 years, ≥ 18 to ≤ 65 years, >65 years), region (US only), and use of stable IVIG or SCIG regimen prior to screening (yes, no).

Prior to closing enrollment early, 66 subjects (about 16~17 subjects per treatment group) were recruited and randomized from US sites.

2.2. Sample Size and Power Considerations

The trial was terminated by sponsor early and the actual sample size for the study was not driven by the number of cases to demonstrate the efficacy of the antibody arm, compared to placebo, in preventing symptomatic (broad term), RT-PCR-confirmed SARS-CoV-2 infection in immunocompromised participants.

The planned number of cases needed to detect the target antibody efficacy and corresponding power with log-rank test are not reached for this study due to early study termination. There's no interim analyses for this study. Study power may not be reached due to early termination.

2.3. Study Plan

The study event table is presented in Section [10.1](#).

3. ANALYSIS POPULATIONS

In accordance with guidance from the International Conference of Harmonization of Technical Requirements for Registration of Pharmaceuticals for Human Use (ICH) guideline ICH E9 Statistical Principles for Clinical Trials ([ICH, 1998](#)), the following population of analysis will be used for all statistical analysis:

3.1. The Efficacy Analysis Sets

The intent-to-treat (ITT) population is defined as all randomized participants.

The primary analysis population for efficacy will be the modified intent-to-treat (mITT) population, defined as all randomized participants who received at least one dose of the study drug and at baseline (day 1):

- Have tested negative by RT-qPCR (central lab results), and
- Have central serology test result (Elecsys® anti-S RBD total Ig) ≤ 50 U/mL

Analysis will be performed according to the study drug allocated (as randomized).

ITT will be used to summarize demographics and baseline characteristics of participants.

3.2. Safety Analysis Set

The safety analysis set (SAF) includes all participants who received any study drug; it is based on the treatment received (as treated). Determination of “as treated” will be based on the actual study drug received. Treatment compliance/administration and all clinical safety variables will be analyzed using the SAF.

3.3. Pharmacokinetic Analysis Set

The PK analysis set is defined for each study drug separately, includes all participants who received active study drug, and who had at least 1 non-missing result of each respective analyte following the first dose of respective study drug. Participants will be analyzed based on the actual treatment received (as treated) rather than as randomized.

Participants who test positive for SARS-CoV-2 infection during the treatment period and discontinue study drug may be analyzed separately.

3.4. Immunogenicity Analysis Sets

The ADA analysis sets (AAS) are defined for each study drug separately and include all participants who received any amount of study drug (active or placebo [safety analysis set]) and had at least one non-missing ADA result following the first dose of the respective study drug or placebo. The AAS are based on the actual treatment received (as treated) rather than as randomized.

The NAb analysis sets (NAbAS) are defined for each study drug separately and include all treated participants (active or placebo) that are included in the ADA analysis set and that tested negative at all ADA sampling times or tested positive at one or more post-dose ADA sampling times and had at least one non-missing post-dose NAb result (either imputed or analysis result).

Samples that tested negative for ADA are not assayed in the NAb assay and the corresponding NAb results are imputed as negative and included as such in the NAb analysis set. Participants in the NAbAS with multiple post-dose ADA results which consist of both imputed NAb-negative result(s) for ADA negative samples and only missing NAb results for all ADA-positive result(s), are set to NAb negative. Participants in the NAbAS that have at least one post-dose positive NAb analysis result are set to NAb positive even if other NAb results are missing.

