### 5.5. Immunogenicity Variables

The immunogenicity variables are ADA status, titer, and NAb status at nominal sampling time/visit. Serum samples for ADA will be collected at the visits specified in [Table 1](#). Samples positive in the ADA assays will be further characterized for ADA titers and for the presence of NAb.

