### **11.3.4. Immunogenicity Analysis Sets**

The ADA analysis sets (AAS) includes all participants who received any amount of study drug (active or placebo [safety analysis set]) and had at least one non-missing ADA result following the first dose of the study drug. The AAS is based on the actual treatment received (as treated) rather than as randomized.

The NAb analysis sets (NAS) includes all treated participants who received any study drug (active or placebo), have at least one non-missing ADA result following the first dose of study drug (active or placebo), and either tested negative at all ADA sampling times or tested positive for ADA with at least one non-missing NAb result after first dose of the study drug (active or placebo). Participants who are ADA negative are set to negative in the NAb analysis set.

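### SAP 3.4 counts some participants with mixed ADA results as NAb negative when none of their ADA-positive samples has a NAb result, so NAb incidence can be lowered but never raised

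*SAP*

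**What the plan says.** NAb testing follows ADA testing. Protocol 5.5 states: "Samples positive in the ADA assays will be further characterized for ADA titers and for the presence of NAb". SAP 3.4 adds the converse: "Samples that tested negative for ADA are not assayed in the NAb assay and the corresponding NAb results are imputed as negative".

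Protocol 11.3.4 admits to the NAb analysis set those treated participants with a post-dose ADA result who "either tested negative at all ADA sampling times or tested positive for ADA with at least one non-missing NAb result after first dose". Its only rule for setting a status without an assay works at participant level: "Participants who are ADA negative are set to negative in the NAb analysis set".

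SAP 3.4 changes both parts. An ADA-positive participant enters the set if they "had at least one non-missing post-dose NAb result (either imputed or analysis result", so an imputed value is enough. It then fixes the status of one group. The group is described as "Participants in the NAbAS with multiple post-dose ADA results which consist of both imputed NAb-negative result(s) for ADA negative samples" together with "only missing NAb results for all ADA-positive result(s), are set to NAb negative".

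SAP 5.10.2 defines a negative NAb status by two routes: a negative ADA assay, or a positive ADA assay followed by a negative NAb assay. It has no category for a sample that is ADA positive with the NAb result missing. SAP 1.2.4 lists the departures from the protocol's statistical section and names only some exploratory efficacy endpoints.

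**The concern.** A negative ADA result in one sample does not show whether the antibodies found in another sample neutralise the drug. If every ADA-positive sample of a participant lacks a NAb result, the only samples that could have shown neutralising activity were not read. SAP 3.4 lets the imputed negative from the ADA-negative sample stand in for them, and so turns an unknown into the favourable category. Elsewhere the SAP leans the other way: in SAP 6.3 a missing severity becomes severe or Grade 3, and a missing relationship becomes related.

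What is at stake is the incidence of NAb to each antibody. This is a secondary endpoint in protocol 4.2, and protocol 3.3.2 names the consequences of immunogenicity, NAb development included, as a potential risk and the reason for sampling. NAb status may also label the concentration profiles in SAP 5.11.1. Because the analyses are descriptive, the printed count is itself the result.

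**Working it through.** The documents give no ADA or NAb rate, so there is no stated figure to reproduce. The check has three steps.

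**1. Where the two rules differ.** The schedule tables are broken in the available text, but they appear to give two post-dose ADA samples, on days 29 and 169. Each sample has five possible states: ADA negative; ADA positive with NAb positive, negative or missing; or no sample. That makes 5 × 5 = 25 ordered patterns. The documents disagree in two of them, which are one situation in either order:

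| Post-dose results | SAP 3.4 | Protocol 11.3.4 |
|---|---|---|
| One ADA negative, one ADA positive with NAb missing | NAb negative | Not in the set |
| Both ADA positive, both NAb missing | Not in the set | Not in the set |
| One sample only, ADA positive, NAb missing | Not in the set | Not in the set |

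**2. Direction.** Let N be the participants in the SAP set for one arm and one antibody, A the ADA-positive participants among them, m those the rule affects, and q the chance of being NAb positive given ADA positive. Assume that NAb results are missing at random among ADA positives. The expected NAb incidence is then:

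- complete data: qA/N
- protocol set: q(A−m)/(N−m)
- SAP: q(A−m)/N

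The SAP figure is (N−m)/N times the protocol-set figure. The protocol-set figure is in turn below the complete-data figure whenever A < N, because it drops ADA positives and keeps every ADA negative. If no positive is observed, the SAP and the protocol set both give 0%.

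**3. Size.** SAP 2.1 gives 66 randomised participants, about 16 to 17 per arm. N, A, m and q below are assumptions.

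- Relative effect against the protocol set, N = 16: 15/16 = 0.938 for m = 1 and 14/16 = 0.875 for m = 2. For N = 17: 16/17 = 0.941 and 15/17 = 0.882. The SAP figure is about 6% to 12% lower in relative terms.
- Absolute effect against the protocol set, N = 16, m = 1, one observed positive: SAP 1/16 = 6.25%, protocol set 1/15 = 6.67%, a difference of 0.4 percentage points.
- Worst case, one affected participant who was truly NAb positive: the loss against complete data is 1/16 = 6.25 or 1/17 = 5.9 percentage points. In the example above, the truth would be 2/16 = 12.5% and the SAP would print 6.25%.
- A larger case, N = 16, A = 4, m = 2, q = 0.5: complete data 2/16 = 12.5%, protocol set 1/14 = 7.14%, SAP 1/16 = 6.25%. Among ADA positives only: complete data 2/4 = 50%, missing results left out 1/2 = 50%, SAP rule 1/4 = 25%.

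The last line bears on the remedy. Under the stated assumption, exclusion leaves a downward bias when the denominator is the whole set. A proportion among ADA positives with an assay result does not have that bias.

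**The case against.** The strongest case against raising this is that it may touch nobody. The rule needs at least two post-dose ADA results of opposite sign. Protocol Table 1, which holds the ADA sampling, no longer applies under Amendment 2, and the close-out schedule in Table 2 lists no ADA sample. A participant moved to close-out before day 169 may have one post-dose result and fall outside the rule. This stands, and it keeps the point minor.

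The status of the endpoint has also changed. SAP section 1 designates all primary and secondary endpoints exploratory, and both documents make all analyses descriptive and say that immunogenicity data may be analysed. This stands too. The protocol also leaves further detail to the SAP, and its entry wording does not say whether an imputed result counts as non-missing. That is fair, but protocol 11.3.4 sets to negative only participants who are ADA negative, and 11.4.7 reserves that status for those negative in all samples. The SAP rule is therefore a departure, and it is not declared.

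It could be said that SAP 5.10.2 works at sample level and that the ADA-negative sample does meet its definition. True, but the ADA-positive sample without a NAb result meets neither route to negative, and it is that sample which leaves the participant's status open.

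Four stronger readings are tempting, and the documents do not support them:

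- A reader might infer that every ADA-positive participant without a NAb result is called negative. Without an ADA-negative post-dose sample, such a participant has neither an imputed nor an assay result and stays outside the set.
- A reader might take 6 percentage points as the effect of the rule against the protocol set. It is the worst case against complete data.
- A reader might conclude that immunogenicity as a whole is understated. ADA status, category and titre are unaffected. The safety association in SAP 5.11.2 uses the NAb-positive group, whose membership the rule does not change.
- A reader might think that returning to the protocol set removes the bias. Step 3 shows that it does not.

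**Conclusion.** The rule is wrong as written, in a narrow group. Participants with mixed post-dose ADA results and no NAb result on any ADA-positive sample have unknown NAb status, and SAP 3.4 reports them as negative. This can lower NAb incidence or leave it unchanged. It conflicts with protocol 11.3.4 and is not listed in SAP 1.2.4.

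The size is small and may be nil: 0.4 percentage points against the protocol set with N = 16, one affected participant and one observed positive, and about 6 points for one participant in the worst case. These figures rest on assumed counts and on the randomised arm size. ADA samples were taken only at participating sites (protocol 9.1.1), so the true N may be lower, and each participant would then weigh more. This is worth correcting because the change is cheap and the rule works in one direction; it does not threaten the study's conclusions.

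**What to change.** Replace the sentence in SAP 3.4. Participants with at least one ADA-positive post-dose sample and no NAb assay result on any such sample should appear in their own row, *ADA positive, NAb not available*, and should not be counted as NAb negative. Reporting this row beside the positives also lets a reader bound the incidence: with 16 participants, one positive and one not available, it lies between 1/16 = 6.25% and 2/16 = 12.5%.

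Add NAb positives as a proportion of ADA-positive participants with a NAb assay result. Then either align the NAb set with protocol 11.3.4, so that an imputed result no longer admits an ADA-positive participant, or list the departure in SAP 1.2.4.

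The cost is one sentence, one table row and one extra proportion, with no new data. The NAb denominator may become slightly smaller. If nobody is affected, no result changes and the two documents agree.
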